## 9.2 Interim analysis

One formal Interim analysis to assess the primary and secondary endpoints of efficacy is planned when the population of patients with available primary efficacy endpoint data is at least 240 patients (120 patients in each group treatment: the main group is Ferrum Lek® (iron (III) hydroxide polymaltosate) and the reference group MALTOFER® (iron (III) hydroxide polymaltosate). Safety and Efficacy will be assessed for all patients who received at least one dose of the randomized treatment at the time of the interim analysis. Based on the results of the interim analysis of the primary and secondary statistical endpoints of the efficacy and safety of the study Sponsor may decide to stop the study if study endpoints have been met as per protocol based on the results of interim analyses or sample size might be recalculated using results of interim analyses.

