Ferrum Lek® (iron (III) hydroxide polymaltosate), 100 mg of tablets (Lek d.d., Slovenia), compared to MALTOFER® (Vi Switzerland), in the treatment of patients with mild and iron-deficiency anaemia.Study objectivesMain Objective: To assess the non-inferiority of the therapeutic efficacy of Lek® 2 tablets daily (200 mg), via assessing the effect on her level in the blood (g/l) after 12 weeks of treatment for pati- iron-deficiency anemia of mild and moderate severity compa MALTOFER® 2 tablets daily (200 mg) during the same per Secondary objectives:	
To assess the non-inferiority of the therapeutic efficacy o Lek ® 2 tablets daily (200 mg), via assessing the effect on her level in the blood (g/l) after 12 weeks of treatment for pati- iron-deficiency anemia of mild and moderate severity compa MALTOFER ® 2 tablets daily (200 mg) during the same per Secondary objectives:	hewable for S.A.,
Lek ® 2 tablets daily (200 mg), via assessing the effect on her level in the blood (g/l) after 12 weeks of treatment for pati- iron-deficiency anemia of mild and moderate severity compa MALTOFER ® 2 tablets daily (200 mg) during the same per Secondary objectives:	
	noglobin ents with ared with
Assessment of safety of Ferrum Lek ® 2 tablets daily (2)	
compared with MALTOFER ® 2 tablets daily (200 mg), frequency, characteristics, intensity and relationship to t received of AEs.	via the
Number of study sites20 sites in the Russian Federation.	

Number of subjects	It is planned to randomize 336 patients (168 patients in each treatment group) considering that no more than 15% of them will drop out before the end of study per protocol.
	Randomization will be stratified by two factors:
	- Gender (male vs female);
	- Hb level (80–94 g/L vs 95–110 g/L)
	Thus, it is necessary to receive data from at least 286 patients (143 patients in each treatment group) who completed the study according to protocol.
Duration of the study	Subject enrollment – not longer than 9 months. Treatment – 3 months (12 weeks). Follow-up visit (by phone) – 14 days after the last planned visit to the study cite. Total study duration – not more than 12 months.
Study design	A phase III, open-label, active-controlled, randomized, multicenter, prospective, comparative, parallel-group study (in the Russian Federation).

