# 4.2.4 Duration of the study

Total duration of the study will be no more than 12 months and will include subjects recruitment (9 months), treatment (3 months) and a Follow-up visit (by phone) 14 days after the end of the active therapy period.

[figure not shown]

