## 5.3 Exclusion criteria

#### 5.3.1 Terms and conditions for the subjects exclusion from the study

The subjects may be excluded from the study on their own free will at any moment, without giving any reason, as well as upon decision of the Investigator or Sponsor in cases when continuation of the participation may inflict harm to the patient's health and/or life. In addition, the patient must be excluded in the cases listed below:

- 1. Negative trend of the disease
- 2. The Ethics Committee, regulatory authorities or Sponsor terminate the study or participation of the specific study site for any reason.
- 3. The Investigator's decision to withdraw the patient from the study in the interests of the patient.
- 4. Withdrawal of the informed consent (unwillingness of the patient to continue his/her participation in the study).
- 5. Serious deviation from the study protocol;
- 6. Individual intolerance of study drugs;
- 7. Clinically significant adverse event or serious adverse event related to investigational drug;
- 8. Patient's non-compliance;
- 9. False inclusion (e.g., the patient was included in breach of the inclusion/non-inclusion criteria);
- 10. The patient complies with the non-inclusion criteria during the study;
- 11. Patient receives/needs additional treatment, which may influence the study results or patient's safety;
- 12. Other conditions or events which, in the Investigator's opinion, require the patient's exclusion from the study.

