## 6.2 Duration of treatment:

Patients in both groups will take drugs daily during 12 weeks.

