All data provided for the evaluation will be integrated into the final clinical study report which will describe the methodology for conducting statistical analysis, as well as clinical conclusions regarding efficacy and safety.

The CS report will be prepared by the CRO in cooperation with the Sponsor. The principal investigator of each study site will receive a copy of the Report for review and subsequent signing. The structure and content of the Report will generally comply with the requirements of the ICH E3 guidelines, as well as applicable local regulatory requirements.

If recalculation of the sample size using the results of the interim analysis is necessary, Report on the interim analysis results will be generated, it will be submitted to the regulatory authority of the Russian Federation with a view to obtaining permission to continue the clinical study involving an increased number of patients.

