9.2. Other safety endpoints

No other safety endpoints are foreseen in this study.

10. Exploratory analysis

In the course of this study, exploratory analysis is not envisaged.

11. Interim analysis

One interim analysis is planned to assess the primary and secondary efficacy endpoints when a group of patients with available data on the primary endpoint will include at least 200 subjects [100 patients in each treatment group: in the main treatment group of patients taking Ferrum Lek[®] (iron (III) hydroxide polymaltosate complex) and in the control group of patients taking MALTOFER[®] (iron (III) hydroxide polymaltosate complex]. Safety and efficacy will be assessed in all patients who have received at least one dose of randomized therapy at the time of the interim analysis. Based on the results of the interim analysis of the primary and secondary statistical endpoints of efficacy and safety, the Sponsor may decide to discontinue the study if the endpoints of the study are achieved in accordance with the protocol based on the results of the interim analyses or the sample size can be recalculated using the results of the interim analysis.

STATISTICAL ANALYSIS PLAN

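### With the planned 9-month recruitment the interim look comes at about or after its end, so a stop saves few or no enrolments and would mainly cut off data from patients already randomised

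*Protocol*

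**What the plan says.** The interim look is triggered by patients with primary-endpoint data. Protocol 9.2 and the synopsis require at least 240 (120 per group). Protocol 9.3, SAP 2.3 and SAP 11 give 200 (100 per group), and Protocol 9.3 and SAP 2.3 also place the look at 70% of the total sample.

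Two actions may follow. Protocol 9.2 says: "Sponsor may decide to stop the study if study endpoints have been met as per protocol based on the results of interim analyses". SAP 11 agrees: "the Sponsor may decide to discontinue the study if the endpoints of the study are achieved in accordance with the protocol". Protocol 9.2 and SAP 11, though not the synopsis, also allow the sample size to be recalculated. Protocol section 12 then requires an interim report to the regulator to obtain "permission to continue the clinical study involving an increased number of patients".

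On timing, the synopsis sets enrolment at "not longer than 9 months". Protocol 4.2.4 says "Total duration of the study will be no more than 12 months and will include subjects recruitment (9 months), treatment (3 months" and adds "a Follow-up visit (by phone) 14 days after the end of the active therapy period". Protocol 6.2 states: "Patients in both groups will take drugs daily during 12 weeks".

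Protocol 5.3.1 lists, among the cases in which a patient must be excluded, item 2: "The Ethics Committee, regulatory authorities or Sponsor terminate the study".

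Neither document gives an expected accrual pattern, a recruitment pause, a time allowance for the interim analysis, or a provision for patients still on treatment if the study stops.

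**The concern.** An efficacy interim usually earns its place by sparing enrolment or by allowing an adjustment while recruitment is still open. Here the endpoint takes 12 weeks to observe and recruitment lasts about three times as long, so most or all patients may be randomised before the look can happen.

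A decision to stop would then act on patients who are already in the trial. If they are excluded when the sponsor terminates, their Week 12 haemoglobin and Day 98 adverse-event follow-up are never obtained. They also cannot meet the per-protocol definition in Protocol 9.8, which requires the full treatment and follow-up period. Safety is the stated secondary objective, so the lost exposure matters. A sample-size increase decided at that point would run past the stated study length.

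**Working it through.** **Inputs.** 336 randomised, 286 completers and 15% withdrawal (Protocol 9.3); recruitment 9 months (4.2.4, synopsis); 84 days to the endpoint and 14 days to the follow-up call (4.2.4, 6.2); triggers 240 and 200. Even accrual is an assumption. A month is taken as 30.44 days, so 84 days = 2.76 months and 14 days = 0.46 month.

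**The plan's own figures.** With margin 5 g/L, SD 15 g/L, zero true difference, 80% power and one-sided 0.025, a fixed design needs 142 per arm. A two-look O'Brien-Fleming design needs about 143 to 144, in line with the stated 143. 286/0.85 = 336.5, against 336 stated. 0.70 × 286 = 200.2, so the 200 trigger matches the 70% look; 240/286 = 84% does not.

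**Time of the look.** The accrual rate is 336/9 = 37.33 per month. The number who must have been randomised is R = trigger/(1 − loss), and look time = R/37.33 + 2.76. The number short of Week 12 is those randomised by the look minus R, counting no early withdrawals among them.

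| Trigger | Loss | R | Look (month) | Randomised by the look | Not yet enrolled | Short of Week 12 |
|---|---|---|---|---|---|---|
| 240 | 15% | 282 | 7.56 + 2.76 = 10.32 | 336 | 0 | 54 |
| 240 | 0% | 240 | 6.43 + 2.76 = 9.19 | 336 | 0 | 96 |
| 200 | 15% | 235 | 6.30 + 2.76 = 9.06 | 336 | 0 | 101 |
| 200 | 0% | 200 | 5.36 + 2.76 = 8.12 | 303 | 33 | 103 |

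**Cleaning and analysis time.** With one further month (an assumption), the number short of Week 12 falls to about 16, 59 and 63 in the first three rows. In the last row recruitment would finish during that month unless paused, so about 99 remain short of Week 12 and the saving of 33 disappears.

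**Other accrual shapes, still over 9 months.** If accrual is slower at the start, the look with 15% loss moves to month 9.5 to 11.0. If it is faster at the start, the look with 15% loss comes at month 7.7 to 8.4 for 200 but still at month 9.5 to 9.9 for 240. The most favourable case run was strongly front-loaded accrual, trigger 200 and no loss. It gives month 6.55 with 78 on treatment, leaving 336 − 200 − 78 = 58 not yet enrolled.

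**Recalculation.** A patient added at the instant of the look finishes follow-up 2.76 + 0.46 = 3.22 months later:
- 200 trigger, 15% loss: 9.06 + 3.22 = month 12.3
- 240 trigger, 15% loss: 10.32 + 3.22 = month 13.5
- 200 trigger, no loss: 8.12 + 3.22 = month 11.3, leaving about 20 days for cleaning, report, permission, screening and all extra enrolment

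**Stated duration.** This needs no accrual assumption. 9 × 30.44 + 84 + 14 = 372 days against 365, or 379 days (about 12.5 months) with 7 days of screening. To finish by month 12 a patient must be randomised by (365.25 − 98)/30.44 = month 8.8.

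**The case against.** **The position relative to the end of recruitment is assumption-dependent.** A reader might infer that the look always follows the end of recruitment. At the 200 trigger with 15% loss the margin is 9.06 against 9.00 months, about two days. The synopsis gives 15% as a ceiling. A 10% loss puts the look at month 8.7, and any loss below about 14% puts it before recruitment ends. Front-loaded accrual does the same. This stands, and so the point is worded as at about or after the end.

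**The number affected.** A reader might infer that a stop always cuts off about 100 patients, or 30% of the trial. That figure belongs to the 200 trigger, or to 240 with no loss. The 240 trigger with the planned 15% loss gives about 54, and no stop can occur on the day the trigger is reached.

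**Data would not be thrown away.** Protocol 9.2 is permissive and assesses everyone who has taken at least one dose by the interim, so data already collected are kept. What would be lost is data not yet collected. The early-termination visit in 5.3.1.1 is written for withdrawal by the patient and cannot supply a Week 12 value.

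**Recalculation is not ruled out.** The 12 months describes the 336-patient plan. An enlargement approved under section 12 could carry a longer duration. Nine months is also a ceiling: with 6 months' recruitment the look falls at month 7.0 to 7.8 (15% loss), and an enlargement might then fit.

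**The interim is cheap and may have other uses.** The final critical value is 1.976 rather than 1.96, and the sample grows by about one patient per arm. The documents do not say that saving enrolment is its purpose, and it could bring the result forward. This stands, and dropping the interim is a trade-off for the sponsor rather than a correction.

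**Conclusion.** The point holds in limited form. On even accrual over the planned 9 months, the look comes at month 9.2 to 10.3 (240) or 8.1 to 9.06 (200), and a stop spares at most about 33 enrolments. Its main effect would be on patients already randomised: about 54 (240, 15% loss), 96 (240, no loss) or 101 to 103 (200) at the data trigger. One assumed month of cleaning cuts this to about 16 to 63 where recruitment has already ended. As 5.3.1 item 2 stands, their remaining Week 12 and Day 98 data would not be collected.

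A recalculated sample would need a longer study than stated if recruitment takes the full 9 months. The documents do not support the stronger statement that it is impossible.

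The duration figures conflict whatever the accrual pattern: 9 months, 3 months and 14 days do not fit within 12 months. The excess is about one week with 84-day treatment, and recruitment of 8.8 months or less would remove it.

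The size of the main effect rests on the accrual shape, the loss rate, the analysis time and which trigger applies. The documents leave the first and third open and contradict themselves on the last.

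**What to change.** 1. Reconcile the 240 and 200 triggers across Protocol 9.2, the synopsis, Protocol 9.3, SAP 2.3 and SAP 11. State the expected calendar time of the look and the accrual assumption behind it.
2. In Protocol 9.2, the synopsis and SAP 11, state that after a positive interim the Week 12 haemoglobin and Day 98 adverse-event data are still collected for all patients already randomised, and that the full-data analysis is reported alongside the interim result. Reconcile this with 5.3.1 item 2. How those patients are treated is for the sponsor and investigators to settle; no treatment rule is proposed here.
3. Correct the total duration to about 12.5 months, or shorten the enrolment ceiling to about 8.8 months. State that any sample-size enlargement carries a revised duration.

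These are mainly wording changes to the protocol and SAP; choosing the shorter enrolment ceiling would also tighten recruitment slightly. The cost is a wait of up to about 3 months after a positive interim for complete data, with visits that are already planned.

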#### 9.1.2 Analysis of the primary efficacy endpoint

#### Primary efficacy endpoint:

• Changes in blood haemoglobin level (g/L) after 12-weeks of iron-deficiency anaemia treatment (during the final visit), as compared with the baseline value (the screening visit) between the study groups.

Analysis of covariance (ANCOVA) will be used as the main method of assessment of the primary endpoint, with baseline haemoglobin value being a covariate and four fixed factors (treatment group, gender, weight and baseline Hb level (80–94 g/L vs 95–110 g/L). Unrestricted least significant differences (LSD) method will be applied to the ANCOVA results with the calculation of least-square (LS) means with 95% CI for LS means for the difference between the study groups. Non-inferiority will be confirmed if the upper limit of the two-sided 95% confidence interval for LS mean will not exceed the pre-defined non-inferiority margin of 5 g/L.

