## 9.3 Target number of the clinical trial subjects with the sample size justification

Calculation of the sample size is based on published works focusing on iron (III) hydroxide polymaltosate efficacy:

- 7) Maltofer Product Information leaflet (http://www.aspenpharma.com.au/product\_info/pi/PI\_Maltofer.pdf)
- 8) Santiago P. Ferrous versus ferric oral iron formulations for the treatment of iron deficiency: a clinical overview. Scientific World Journal. 2012;2012:846824.
- 9) Geisser P. Safety and efficacy of iron(III)-hydroxide polymaltose complex / a review of over 25 years' experience. Arzneimittelforschung. 2007;57(6A):439-52;

Based on the data of these publications, during 12-weeks of oral administration of iron (III) hydroxide polymaltosate the hemoglobin level can increase on average by 8-15 g/L with a standard deviation up to 15 g/L. As similar efficacy is expected in both groups, zero difference in primary efficacy parameter will be used for calculation of sample size. Maximum value of standard deviation was used -15 g/L to take a maximum variability of the primary endpoint variable into account for properly powered study.

The value of 5 g/L was selected as the non-inferior efficacy limit (in accordance with the limit stated and justified in the above mentioned works.

Thus, the following assumptions were proposed for calculations:

- 10) Changes in blood hemoglobin level (g/L) after 12-weeks of iron-deficiency anemia treatment (during the final visit), as compared with the baseline value (the screening visit 0) are expected to be similar for the investigational and reference drug groups (i.e. expected difference between the two groups is set to zero).
- 11) The pooled standard deviation for the changes in hemoglobin level was 15 g/L.

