- 12) Non-inferiority margin is 5 g/L.
- 13) The significance level (two-sided, in accordance with FDA recommendations) is 95%, which corresponds to the type I one-sided error 0.05.
- 14) Power of the study is 80%, which corresponds to the type II error 0.20.
- 15) Statistical hypotheses evidence of a non-inferior efficacy:

- 16) The ratio between the study and control group sizes is 1:1
- 17) Interim analysis will be performed at 70% of the total sample size
- 18) O'Brien-Fleming alpha-spending function will be used with 80% power for efficacy boundary that will correspond to the following critical values for t-test: 2,628 for interim analysis (corresponds to p=0,005) and 1,976 for final analysis (corresponds to p=0,0245);

Calculation was performed using the clinfun package of Microsoft R Open software (available at https://mran.microsoft.com – Microsoft R Application network), that uses the group sequential design approach for the calculation of fixed sample sizes for the interim and final analysis. According to the output from the clinfun package, 143 subjects per group (286 subjects in total) should complete the study in order to confirm non-inferiority. 200 (100 per group) subjects should have evaluable data to perform interim analysis. Taking 15% withdrawal rate into account, one need to randomize 336 subjects (168 subjects per group). Taking 30% screening failure rate, up to 480 subjects should be screened to achieve target randomization.

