- 2) A pooled standard deviation for the changes in hemoglobin levels was 15 g/L.
- 3) The non-inferiority margin is 5 g/L.
- 4) The significance level (two-sided, according to the recommendations by the Food and Drug Administration) is 95%, which corresponds to a one-sided type I error of 0.05.
- 5) The study power is 80%, which corresponds to a type II error of 0.20.
- 6) Statistical hypotheses are the demonstration of non-inferiority:

$$\mu A - \mu B > 5.0$$

- 7) The ratio between the test and control group sizes is 1:1.
- 8) The interim analysis will be conducted when 70% of the total sample size is reached.
- 9) The O'Brian-Fleming alpha-spending function will be applied with 80% power for the efficiency frontier, which will satisfy the following critical values of the t-test: 2.628 for the intermediate analysis (corresponding to p = 0.005) and 1.976 for the final analysis (corresponding to p = 0.0245).

STATISTICAL ANALYSIS PLAN

Calculations were performed using the clinfun package of the R software, in which the calculation of a fixed sample size for interim and final analyses was performed using the group sequential design.

According to the data obtained with the clinfun package, 143 subjects in each group (total: 286 subjects) should complete the study to confirm the hypothesis of non-inferiority. For the interim analysis, data for 200 subjects (100 in each group) that are suitable for analysis should be obtained. Taking into account the frequency of premature discontinuation of the study, which is 15%, it is necessary to randomize 336 people (168 people in each group). Taking into consideration the withdrawal rate based on the results of the screening that equals to 30%, about 480 people should undergo screening to achieve the target level of randomization.

3. General analysis values

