8.1. Primary endpoint analysis

• Changes in hemoglobin level (g/L) after 12 weeks of iron deficiency therapy (at the final visit) as compared to baseline (determined at the screening visit) in the study groups.

STATISTICAL ANALYSIS PLAN

The covariance analysis (ANCOVA) will be used as the main method for assessing the primary endpoint, with the baseline blood hemoglobin level as a covariate, and four fixed factors (treatment group, sex, weight, and baseline hemoglobin level (80-94 g/L vs. 95-110 g/L). The method of unrestricted least significant differences (LSD) will be applied to ANCOVA results with LS mean values from 95% CI for mean values calculated by the method of least squares for differences between the studied groups. Due to the obvious dependence of the covariates and the base hemoglobin factor (80-94 g/L compared to 95-110 g/L), a linear model containing the term of interaction between these variables will be used.

Non-inferiority will be confirmed if the upper bound of a two-sided confidence interval for the mean value calculated by the method of least squares does not exceed the predetermined non-inferiority margin of 5 g/L. The CI percentage will be determined by the moment of the analysis (interim/final) in accordance with clause 2.3 of the Statistical Analysis Plan.

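### If the trial stops at the interim look, the only planned estimate is the interim LS-mean difference, which on average flatters Ferrum Lek; the complete Week 12 data should be reported beside it

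*Protocol*

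**What the plan says.** Protocol 9.2 plans one formal interim analysis, after which the "Sponsor may decide to stop the study if study endpoints have been met as per protocol". SAP 11 says the same. Both also allow the sample size to be recalculated.

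The primary estimate comes from an ANCOVA. Protocol 9.1.2 specifies "calculation of least-square (LS) means with 95% CI for LS means for the difference between the study groups". SAP 8.1 keeps that estimate and adds one provision for the interim: "The CI percentage will be determined by the moment of the analysis (interim/final"), with a reference to SAP 2.3. There the critical values are "2.628 for the intermediate analysis" and 1.976 for the final one.

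The interim size is not consistent. The protocol synopsis (interim row) and Protocol 9.2 give 240 patients (120 per arm). Protocol 9.3, SAP 2.3 and SAP 11 give 200 (100 per arm).

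Neither document gives a bias-adjusted estimate or a caveat on the point estimate after an early stop. Neither says how Week 12 data arriving after the look from patients already randomised would enter the primary estimate.

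**The concern.** An efficacy boundary selects. The trial stops only when the interim difference happens to be favourable enough, so among stopped trials the ordinary estimate is too favourable to the test product on average. Changing the confidence level protects the test but leaves the point estimate where it was.

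The published size of the difference is what is at stake. Readers and later pooled analyses use that figure as well as the non-inferiority verdict. Stopping is also not a rare event: on the design assumptions the boundary is crossed at the look in 39% of trials at 100 per arm and 48% at 120 per arm.

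**Working it through.** **Inputs.** From Protocol 9.3 and SAP 2.3: "The pooled standard deviation for the changes in hemoglobin level was 15 g/L", described there as the maximum; margin 5 g/L; "expected difference between the two groups is set to zero"; "Power of the study is 80%, which corresponds to the type II error 0.20"; 143 completers per arm; critical values 2.628 and 1.976. Interim size is 100 or 120 per arm. Let d be Ferrum Lek minus Maltofer, the intended direction of the test.

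**1. The plan's own figure.** n per arm = 2 × 15² × (1.960 + 0.842)² / 5² = 18 × 7.85 = 141.3, so 142, against 143 stated. Protocol 9.3 also says "The significance level (two-sided, in accordance with FDA recommendations) is 95%, which corresponds to the type I one-sided error 0.05". Taken literally, that gives 18 × (1.645 + 0.842)² = 111.3, so 112, which does not reproduce the plan. The design is therefore one-sided 0.025. A bivariate-normal calculation with the stated boundaries gives overall one-sided error 0.0250 and power 0.8025 (looks at 100 and 143 per arm), or 0.0243 and 0.8011 (120 and 143).

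**2. Where the trial stops.** SE₁ = SD × √(2/n₁). The boundary is crossed when (d + 5)/SE₁ > 2.628, that is, d > −5 + 2.628 × SE₁.
- 100 per arm: SE₁ = 15 × √0.02 = 2.121; cut-off = −5 + 5.575 = +0.575.
- 120 per arm: SE₁ = 1.936; cut-off = −5 + 5.089 = +0.089.

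**3. Mean reported difference given a stop, true difference 0.** With a = cut-off/SE₁, P(stop) = 1 − Φ(a) and E[d | stop] = SE₁ × φ(a)/(1 − Φ(a)). Rows below SD 15 are assumptions, because the plan gives no ANCOVA residual SD.

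| SD | per arm | cut-off | P(stop) | mean given stop (g/L) |
|---|---|---|---|---|
| 15 | 100 | +0.575 | 0.393 | 2.07 |
| 15 | 120 | +0.089 | 0.482 | 1.60 |
| 12 | 100 | −0.540 | 0.625 | 1.03 |
| 12 | 120 | −0.929 | 0.726 | 0.71 |
| 10 | 100 | −1.283 | 0.818 | 0.46 |
| 10 | 120 | −1.607 | 0.893 | 0.27 |

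A simulation of 2,000,000 trials at SD 15 agrees (2.07 and 1.60). If Ferrum Lek is truly 1 g/L worse (SD 15, 100 per arm), the trial stops 23% of the time and reports +1.81 on average.

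**4. Average over all trials, stopped or not.** Bias = P(stop) × E[d | stop] × (1 − n₁/143). At SD 15 this is 0.393 × 2.07 × 0.301 = 0.25 g/L at 100 per arm, and 0.482 × 1.60 × 0.161 = 0.12 g/L at 120.

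**5. Data that will exist after a stop.** Assume uniform accrual over the planned 9 months and 15% dropout. Evaluable patients enter at 336/9 × 0.85 = 31.7 per month. The 200th reaches Week 12 at 200/31.7 + 2.8 = month 9.1, and the 240th at 240/31.7 + 2.8 = month 10.3. In either case all 336 are already randomised. Complete data give 336 × 0.85 ≈ 286, or 143 per arm:
- SE = 15 × √(2/143) = 1.77, against 2.12 at a look with 100 per arm.
- The later patients are not selected, so the conditional mean becomes (100/143) × 2.07 = 1.45 g/L. For a look at 120 per arm it is (120/143) × 1.60 = 1.34 g/L.

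**The case against.** The strongest case against acting is that nothing decided by the trial changes. The primary objective is a non-inferiority verdict, and its error rate holds with the stated boundaries. A reader might infer that a biased estimate undermines that verdict; step 1 shows it does not.

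The larger figures are also a high-end case. SD 15 is the plan's maximum, taken for raw change, whereas the reported estimate is covariate-adjusted. A reader might take 1 to 2 g/L as a general result, or conclude that a stopped trial must show Ferrum Lek numerically ahead. Neither is supported: with a residual SD of 12 the cut-off is already below zero, and at 120 per arm the mean overstatement is 0.71. Stopping is optional too, and rests on secondary endpoints and safety as well as the primary result, so the figures assume a stop at every crossing. All of this stands and limits the size of the point. It does not remove it.

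A reader might also expect a stagewise-ordered median-unbiased estimate to be the remedy. It would change nothing here. For a stop at the first of two looks, the stagewise p-value is the fixed-sample one, so an observed +0.60 returns +0.60. Its 95% interval is the ordinary one, −3.56 to +4.76. The interval SAP 8.1 calls for at 2.628 is wider, with lower limit 0.60 − 2.628 × 2.121 = −4.97. Adopting the stagewise interval would leave the estimate alone and make the interim interval less cautious.

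**Conclusion.** The point holds as a matter of reporting. After an interim stop with truly equal products, the planned estimate favours Ferrum Lek on average by 2.1 g/L (100 per arm) or 1.6 g/L (120 per arm) at SD 15, which is 41% or 32% of the margin. With an assumed residual SD of 10 to 12 it is about 0.3 to 1.0 g/L. These figures assume a stop at every crossing. They also rest on the intended direction of the test, because the printed hypotheses are unclear on sign. Over all trials the bias is about 0.1 to 0.25 g/L.

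The estimate is adjusted for covariates, and its interval for the look; what is missing is any allowance for stopping in the point estimate. Re-analysis with complete data reduces the conditional bias but does not remove it (2.07 to 1.45 g/L). If the complete-data estimate is reported whether or not the boundary is crossed, there is no stopping bias on average over all trials.

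**What to change.** In SAP 8.1 and SAP 11:
1. Keep the interim test and its look-specific interval as the basis for the decision.
2. If the boundary is crossed, repeat the primary ANCOVA once all patients already randomised have reached Week 12, and report that LS-mean difference with its interval beside the interim one.
3. State that the interim estimate is subject to stopping bias in favour of the test product.
4. Do not substitute a stagewise median-unbiased estimate or its 95% interval.

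Reconcile the interim size (200 or 240) at the same time. Protocol 5.3.1 lists termination of the study by the sponsor among the grounds for excluding a patient. The new wording must be reconciled with that passage, since the re-analysis needs the Week 12 haemoglobin of patients still in the study at the look.

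The cost is SAP wording and completing follow-up already in progress. Under the accrual assumption above, the last patient reaches Week 12 at about month 9 + 2.8 = 11.8, within the planned 12 months.
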